RESEARCH PROPOSAL

Title: Immediate Effect Of Standing Trunk Extension Postures On Spinal Height And Clinical Outcome Measures In Low Back Pain: A Randomized Clinical Trial

Investigators:

[name], PT, ScD - PI

[name], PT, DPT

[name], PT, PhD

Clinical Musculoskeletal Research Laboratory, Center for Rehabilitation Research, School of Health Professions, TTUHSC, Lubbock, TX, USA

TABLE OF CONTENTS

ABSTRACT.....4

LIST OF FIGURES.....5

LIST OF ABBREVIATIONS.....6

BACKGROUND.....7

PURPOSE, AIMS, VALUES.....12

RESEARCH QUESTIONS.....13

HYPOTHESES.....13

COMPARISON VARIABLES.....14

 Independent Variables.....14

 Dependent Variables.....15

 Relationship Variables.....15

METHODS.....16

 Research Design.....16

 Pre-Study Approvals.....16

 Subjects.....16

 Testing Sequence.....17

DATA ANALYSIS.....22

RESEARCH PROJECT TIMELINE.....25

REFERENCES.....26

APPENDICES.....41

ABSTRACT

Background: Standing trunk extension postures have been used for many years as a mechanical approach to low back pain (LBP), sometimes directed by therapeutic intervention, sometimes subconsciously performed by patients to relieve LBP. However, no study to date has investigated the effect of standing trunk extension postures on spinal height and clinical outcome measures.

Objective: The purpose of this study will be to evaluate in subjects with LBP following a period of trunk loading, how spinal height and/or pain, symptoms' centralization, and function outcome measures respond to: (1) standing repetitive trunk extension posture; and (2) standing sustained trunk extension posture. Lumbar range of motion (ROM) achieved during these two trunk extension postures will be compared to spinal height and outcome measures.

Methods: A pre-test, post-test comparison group design (randomized clinical trial) will be used to determine how spinal height changes in response to sustained and repetitive standing trunk extension after a period of spinal loading. The study will use a 2 (between subjects – type of trunk extension: sustained vs. repetitive) x 3 (within subjects - time: before vs. after vs. 2 weeks after intervention) mixed design to evaluate the effects of sustained and repetitive trunk extension in standing on spinal height, pain, symptoms' centralization and function.

Statistical Analysis: A 2(Strategy) X 3(Time) mixed ANOVA will be used to statistically identify significant interactions and main effects for spinal height, pain and function outcome measures. Post-hoc pairwise comparisons will be used to locate significant differences between the different conditions (Time). Significance will be set at $\alpha = 0.05$. Pearson product-moment correlations will be used to measure correlations between lumbar ROM in relation to spinal height and outcome measures. The Kruskal-Wallis 1-factor ANOVA for difference scores will be used to determine changes of intensity and location of symptoms following sustained versus repetitive standing trunk extension. Spearman Rank correlation will be used to evaluate the relationship between spinal height changes and changes of pain and location of symptoms for each group.

Word Count: 326

Key Words: Standing postures; trunk extension; spinal height change; stadiometer

Lay Summary

Standing back extension postures have been used for many years to treat people with low back pain.

No study to date has investigated the effect of standing back extension postures on trunk height, pain and function.

The **purpose** of this study will be to evaluate in subjects with low back pain how trunk height, pain and function respond to standing repetitive versus sustained trunk extension postures.

Methods: A randomized clinical trial will be used to determine how trunk height, low back pain and function change in response to sustained and repetitive standing trunk extension after a period of spinal loading.

Statistical Analysis will be used to measure the outcomes.

LIST OF FIGURES

Figure 1: Flowchart depicting testing sequence.....31

Figure 2: Starting position for standing trunk extension (repetitive and sustained).....34

Figure 3: Sustained trunk extension position and end position of repetitive trunk extension.....35

Figure 4: Position of subject for spinal height measure in stadiometer unit.....36

Figure 5: Position of subject during spinal loading time in sitting.....37

Figure 6: Home exercise program for repetitive trunk extension group.....38

Figure 7: Home exercise program for sustained trunk extension group.....39

Figure 8: Home instructions for each subject.....40

LIST OF ABBREVIATIONS

Analysis of Variance.....	ANOVA
Fear Avoidance Belief Questionnaire.....	FABQ
Intervertebral Disc.....	IVD
Institutional Review Board.....	IRB
Low Back Pain.....	LBP
Numerical Pain Rating Scale.....	NPRS
Range of Motion.....	ROM
Standard Deviation.....	SD
Research Question.....	RQ
Research Hypotheses.....	RH
Independent Variable.....	IV
Dependent Variable.....	DV
Relationship Variable.....	RV

BACKGROUND

According to the United States Department of Labor, there were more than one million injuries and illnesses requiring days away from work amongst private industry, state and local government employees. Among these injuries and illnesses, 16.6 % were low back related equating to 191,479 low back injuries requiring days away from work (US Department of Labor, Bureau of Labor Statistics, 2016). An analysis funded by the National Institute of Health found that the cost of pain outweighed the cost of cancer and diabetes by thirty percent. The authors further reported that the annual cost of pharmaceuticals for pain management was \$16.4 billion, and the cost of lumbar surgeries was \$2.9 billion. Pain indirect costs estimates were \$18.9 billion for disability compensation and \$6.9 billion for productivity loss (Gaskin 2011, The Economic Costs of Pain in the United States).

A joint clinical practice guideline developed by the American College of Physicians and the American Pain Society classified low back pain (LBP) into three categories: (1) nonspecific LBP; (2) LBP potentially associated with radiculopathy or spinal stenosis; and (3) LBP potentially associated with another specific spinal cause. Of those three, lumbar intervertebral disc (IVD) herniation is one of the most common spinal degenerative disorders leading to LBP associated with radiculopathy (Chou 2007, Goupille 1998, McCall 2000). In order to better understand the IVD's role in the development or persistence of LBP and spinal stenosis, there have been many stadiometric studies primarily focused on lumbar spinal height changes associated with various positions and movements

(Kourtis 2004; Magnusson 1996; Lazzarini 2014; Simmerman 2011). These studies stem from IVD height preservation in the aging spine. Natural IVD height preservation is so important that the biomedical field has examined the use of growth factors for IVD biologic regeneration (Masuda 2004) in order to more naturally preserve IVD biomechanical and physiological function as opposed to surgical disruption. To further understand IVD functional properties, researchers have studied the IVD hydraulic permeability and the influence that age and/or degeneration have on fluid movement (Gu 1999). The authors reported that with IVD degeneration, the radial permeability of the annulus fibrosus decreased, mainly because of reduced water content. However, the axial and circumferential permeability coefficients increased, mainly due to structural change, leading to greater IVD isotropic permeability behavior (Gu 1999).

Sixty one percent of time in the work and home environment is spent in the standing posture (US Department of Labor, Bureau of Labor Statistics, 2016). Although prolonged weight bearing postures, such as standing and walking, have been associated with decreased spine height (Tyrrell 1985, Puntumetakul et al 2009), some studies reported that seated weight bearing postures could result in spine height gain (Magnusson 1996a). Sustained and repetitive lumbar extension postures frequently occur after periods of prolonged unloading such as sleep. These postures are periodically repeated throughout the day during activities such as standing and walking (US Department of Labor Bureau of Labor Statistics 2016).

People presenting with directional preferences that include lumbar

extension tend to respond well to exercises geared toward trunk extension (Stankovic 1990, Swinkels 2009, Oliveira 2012). Significant and rapid changes in central and distal pain intensity and location have resulted from standing end-range trunk extension in patients with low back and referred pain (Donelson 1991). Additional studies reported that standing back extension exercises resulted in back pain episodes' prevention and decreased back pain in care workers (Matsudaira 2015; Dunsford 2011). Standing exercises have the advantage to be functional and easily performed in work and home settings (Tonosu 2016).

A positive relationship has been found between lumbar extension range of motion (ROM) and the centralization process in patients with LBP (Bybee et al 2009). The centralization phenomenon is part of the clinical examination findings used to identify specific treatment-based classification subgroups. Centralization is characterized by spinal pain and referred symptoms that are progressively abolished in a distal to proximal direction in response to therapeutic interventions including unloading or specific movement strategies (Brennan et al 2006, Laslett et al 2005). The operational definition and measurement techniques for centralization have been laid out in several studies (Aina et al 2004, Werneke et al 2008). A decreased spinal ROM is commonly associated with low back complications, and functional ROM needs to be restored to allow for the return to previous activity levels (Battie 1987, Vaisy 2015). Several methods have been used to increase spinal ROM including static, repeated, passive postures, and proprioceptive neuromuscular facilitation. Both standing and prone lumbar

extension postures are effective for treating low back Dysfunction Syndrome (McKenzie 2003). However, which method is best suited for increasing spinal ROM remains debated (Sady 1982; Nordez 2017). One author found static prone postures to increase ROM more effectively with 30-60 second sustained postures as compared to 15-second postures, but no difference between the effectiveness of 30-second and 60-second postures (Bandy 1994; Page 2012).

Repetitive postures are another method used to increase ROM by elongating shortened connective tissue. The McKenzie classification of Dysfunction Syndrome is defined as the condition in which adaptive shortening of soft tissues and resultant loss of mobility cause pain by stretching shortened tissues that block full end-range movement (Hefford 2008). Poor postural habits, previous trauma and inflammatory or degenerative processes can lead to this dysfunction. These patients can develop contraction, scarring, adherence and adaptive shortening or imperfect repair and pain is felt when the abnormal tissue is stretched.

Treatment of the Dysfunction Syndrome consists of postural correction, along with repeated end-range movements to remodel contracted structures. This intermittent stress is reported to provide an adequate stretching effect and is most effective in the treatment of extension dysfunction (McKenzie 2003). One study found that patients with LBP chose to perform their extension posture for home exercise in standing 80.8 % of the time and only 19.2 % of the time in the prone position, resulting in similar clinical outcomes where both groups showed equal improvements in lumbar extension ROM (Bybee et al 2008).

Previous studies investigated the effects of postures and movements in lying (unloaded) or seated positions on spinal height (Owens 2009, Gerke et al 2010; Pape 2018). These studies primarily focused on spinal height following static patient positioning and showed that both the lying and supported seated positions resulted in mean spinal height gains of 2 to 5 mm. However, most rehabilitation programs focused on LBP prevention and management use both repetitive and/or sustained spinal extension exercises to improve patients' outcomes (Peterson 2015, Surkitt 2012). Such exercises can be performed in lying or standing position. Although patients with acute and recurrent low back and referred pain tend to respond well to directionally preferred postures (Machado 2006), subjects with chronic symptoms tend to display greater signs of sensitization, biopsychosocial issues (Huysmans 2017), and tend to respond less favorably to directional preferences postures and exercises (Garcia 2017). In order to assess the biopsychosocial effect on clinical outcomes during this study, every subject will complete the Fear Avoidance Belief Questionnaire (FABQ) (Cleland et al 2008).

No study to date has investigated the effects of standing extension postures on spinal height, pain, centralization and function. Therefore, the purposes of this study will be to evaluate in a sample of LBP patients the effect of standing trunk extension, both sustained and repetitive, following a period of spinal loading, on (1) spinal height; (2) pain; (3) symptoms centralization and (4) functional measures.

PURPOSE, AIMS, VALUES

Purpose(s):

The purpose of this study is to assess the effect of commonly used standing trunk extension postures on spinal height as well as pain, symptoms' centralization, and function in patients with LBP.

Aim(s):

Our aim is to better understand the effect of standing sustained and repetitive trunk extensions on spinal height and LBP patients' symptoms intensity, centralization and function. With many patients commonly falling into a directional preference group and responding positively to mechanical spinal input, it is our aim to investigate if such trunk extension postures performed in standing affect spinal height in regard to growth or shrinkage and if these changes are associated with symptoms intensity, centralization and functional alterations.

Value(s):

No previous study has examined changes in spinal height following standing trunk extension postures and little is known on the effect of such standing postures on spinal height. The results of this study could impact rehabilitation programs that include standing trunk extension as a means of therapeutic intervention. This is valuable especially in aging population with degenerated IVD's, loss of IVD height and propensities toward spinal stenosis, as we do not know if those subjects with directional preferences toward spinal extension could use standing trunk extension postures at home or in the work

environment to grow and/or prevent spinal shrinkage.

RESEARCH QUESTIONS, HYPOTHESES AND VARIABLES

Research Question(s) (RQs)-This project aims to answer the following research questions:

1. **RQ 1:** Does sustained and repetitive standing trunk extension following a period of spinal loading effect spinal height, pain, centralization and function testing outcomes immediately and two weeks following the interventions in patients with LBP?
2. **RQ 2:** Following a period a spinal loading, is there a difference in spinal height, pain, centralization and function testing outcome *changes* immediately and two weeks following sustained and repetitive standing trunk extension postures in patients with LBP?
3. **RQ 3:** Is there a correlation between the degree of trunk extension during standing lumbar extension posture and spinal height, pain, centralization and function testing outcomes *changes* immediately and two weeks following the interventions in patients with LBP?

Research Hypotheses- (RH)This student has devised the following research hypotheses:

1. **RH 1:** It is expected that following a period of trunk loading, both sustained and repetitive trunk extension postures in standing will result in increased spinal height, reduced pain, enhanced centralization and

function testing outcomes immediately and two weeks following the interventions in patients with LBP.

2. **RH 2:** It is expected that following a period of trunk loading, sustained standing trunk extension posture in standing will result in greater spinal height gain as compared to repetitive standing trunk extension postures, while repetitive standing trunk extension postures will result in greater improvements in pain, centralization and function testing outcomes as compared to sustained standing trunk extension postures immediately and two weeks following the interventions.
3. **RH 3:** It is expected that following a period of trunk loading, there will be a positive correlation between the degree of trunk extension during standing trunk extension posture and spinal height, centralization, pain and function testing outcomes changes immediately and two weeks following the interventions in patients with LBP.

Comparison Variables

Independent Variable(s)-The student plans to use the following Independent variable(s) (IV)

1. IV1: Trunk extension
 - a. IV1: sustained
 - b. IV2: repetitive
2. IV2: Time

- a. IV1: before
- b. IV2: after (immediately)
- c. IV3: after 2 weeks

Dependent Variable(s)-The Student plans to measure the following dependent variable(s) (DV)

1. DV1: Spinal height using stadiometer (ratio scale).
2. DV2: Pain rating using numerical pain rating scale (NPRS) (ordinal scale).
3. DV3: Centralization (ordinal) using body diagram.
4. DV4: Modified Oswestry Pain Disability Questionnaire (ordinal scale)

Relationship Variable(s)- (RV) (if applicable)

1. RV1: Degree of spinal extension (ratio)
2. RV2: Spinal height using stadiometer (ratio scale).
3. RV3: Pain rating using numerical pain rating scale (NPRS) (ordinal scale).
4. RV4: centralization (ordinal).
5. RV5: Modified Oswestry Pain Disability Questionnaire (ordinal scale)

METHODS

Research Design(s)

A pre-test, post-test comparison group design (randomized clinical trial) will be used to determine how spinal height changes in response to sustained and repetitive standing trunk extension after a period of spinal loading. The study will use a 2 (between subjects – type of trunk extension: sustained vs. repetitive) x 3 (within subjects - time: before vs. after vs. 2 weeks after) mixed design to evaluate the effects of sustained and repetitive trunk extension in standing on spinal height, pain, centralization and function outcome measures.

Pre-study Approvals

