defined as either (1) a specific direction of trunk movement or posture noted during the physical examination or (2) a specific easing factor reported by the patient during the subjective history that alleviates or decreases the patient's pain, with or without the pain having changed location and/or increased the patient's lumbar range of motion (Werneke 2011). A questionnaire including pertinent medical history will be completed (Appendix C). Subjects will complete (1) a Numerical Pain Rating Scale (NPRS) to rate their current, minimum, maximum and average LBP over the last two days (Ferreira-Valente MA 2011) as well as paresthesia signs/symptoms intensity (Appendix D); (2) Body Diagram for indicating location of symptoms (Appendix E); (3) Modified Oswestry low back pain questionnaire (Fritz 2001) (Appendix F); (4) Fear Avoidance Belief Questionnaire (Cleland et al 2008) (Appendix G). A researcher will record subject's height and weight. A Flow chart illustrates study sequence in details (Figure 1).

If the subject meets criteria for inclusion in the study, the subject will complete a familiarization procedure to determine the consistency to reposition themselves in the stadiometer. Subjects able to reposition themselves in the stadiometer with a SD of 1.3mm or less for five consecutive measurements (Stothart et al 2000; Gerke et al 2011; Owens et al 2009) will be included in the study. The digital display will be covered to blind the researcher performing the measurements. The data will be automatically recorded by the stadiometer and manually downloaded to a laptop computer.

At the beginning of data collection, a randomization plan generator

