The subject will reposition on the stadiometer and spinal height will be measured (Measurement 4). Trunk extension will be measured to determine the strength of correlations between the degree of trunk extension during standing trunk extension posture and spinal height, pain and centralization testing outcomes changes (MacDermid et al 2015). The subject will score their low back and lower extremity symptoms using NPRS (Ferreira-Valente MA 2011), and *map their pain* on a body pain diagram (Appendix E) prior to intervention, immediately after and 2-week following the intervention to determine pain rating and centralization of symptoms (Simmerman et al 2011). The principal investigator will apply a numeric overlay template to the patient's body diagrams to document the most distal pain location scores between 1 and 6 (Appendix I). Higher score will indicate a more distal symptoms' location.

Home instructions

Subjects will be instructed to continue to use their medications, including medications aimed at decreasing their pain, as prescribed by their primary healthcare provider and not to change them during the follow-up two-week period. A sheet including home exercise instructions will be provided to each patient. Instructions will include repetitive or sustained trunk extension based on random group assignment, performed approximately 5 times per day. Each subject will complete a sheet recording home exercise compliance upon arrival in

session 2 (Appendix I).

Session 2

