changes in spinal height, degrees of spinal extension, pain, and function outcomes.

For *experimental hypothesis 1*, a paired-t-test (or Wilcoxon sign-rank test if the data do not meet assumptions for parametric inferential statistics) will be used to assess differences in spinal height, centralization and pain outcomes improvements following sustained and repetitive trunk extension postures.

For *experimental hypothesis 2*, 2 (between subjects - type of trunk extension: sustained vs. repetitive) x 3 (within subjects - time: before, immediately after and 2-week after) mixed ANOVA's will examine differences in (1) spinal height; (2) pain; and (3) function outcomes, as a result of sustained and repetitive standing trunk extension after a period of spinal loading. Post hoc paired t-tests will explore further for significant differences in spinal height, pain and function outcomes between the six conditions.

Experimental hypothesis 3 will be tested with Pearson product-moment correlations to determine the strength of correlations between the degree of trunk extension during standing trunk extension posture and spinal height, pain and function, outcomes changes in patients with LBP.

Spearman's Rank Order correlation will be used to determine the strength of the correlation between centralization and the degree of trunk extension posture in standing.

Alpha level will be set at 0.05 for significance for all tests and Bonferroni corrections performed as needed.

REFERENCES

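### RH2, pain and function: the planned arm comparison rests on change scores; adjusting for the baseline scores already collected would be more precise at no extra data cost

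*Combined protocol and SAP*

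**What the plan says.** RH2 (Research Hypotheses) is a between-arm claim about improvement. For the clinical outcomes, "repetitive standing trunk extension postures will result in greater improvements in pain, centralization and function testing outcomes" than the sustained posture, both immediately and at two weeks. RQ2 likewise asks about differences in outcome changes.

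The test is in Data Analysis, Inferential analyses, under experimental hypothesis 2: a factorial with two postures by "3 (within subjects - time: before, immediately after and 2-week after) mixed ANOVA's will examine differences in" spinal height, pain and function. The Abstract describes the same model and says the "mixed ANOVA will be used to statistically identify significant interactions and main effects for spinal height, pain and function outcome measures". Baseline is thus a level of the outcome.

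Neither follow-up analysis uses baseline as a covariate:

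- Data Analysis: "Post hoc paired t-tests will explore further for significant differences in spinal height, pain and function outcomes between the six conditions".
- Abstract only: "The Kruskal-Wallis 1-factor ANOVA for difference scores will be used to determine changes of intensity and location of symptoms".

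The baseline data exist. Under Testing Sequence, Session 1, pain is rated "prior to intervention, immediately after and 2-week following the intervention to determine pain rating and centralization of symptoms". The "Modified Oswestry low back pain questionnaire" is completed before the intervention in Session 1 and again at the start of Session 2. No administration is scheduled straight after the Session 1 intervention, so function has two values and not three.

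**The concern.** When the pre-treatment score is a Time level and its mean is left free in each arm, the Strategy x Time test subtracts baseline in full. Subtraction is the best use of a baseline only when it predicts the follow-up score one for one. At lower correlations it carries baseline noise into the arm comparison. A covariate removes only the part of baseline that predicts follow-up.

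Subjects / Specimens plans for 40 completers and gives no power calculation. In a trial of that size, avoidable variance in the arm difference widens the interval for pain and function and makes a null result harder to interpret.

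The plan also does not say which ANOVA effect decides RH2, although the Abstract lists main effects among those to be identified.

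**Working it through.** **The plan's own figure.** The target of 40 completers has no stated effect size, SD or power, so it cannot be reproduced, confirmed or contradicted.

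**Inputs.** From the documents: 40 completers, alpha 0.05, three NPRS times, two Oswestry times. Assumed: 1:1 allocation (20 per arm), two-sided tests, equal variances (SD scaled to 1), a common correlation r between any two times (0.3, 0.5, 0.7), and an arm difference of 0.75 SD, the same at both follow-up times.

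**One follow-up time** (2-week Oswestry, or NPRS at either time). Variance of the relevant quantity per subject:

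- Change score: 2(1-r) = 1.40, 1.00, 0.60
- Baseline-adjusted (ANCOVA): 1-r² = 0.91, 0.75, 0.51
- Ratio: (1-r²)/[2(1-r)] = (1+r)/2 = 0.65, 0.75, 0.85

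With two Oswestry values, the Strategy x Time test is exactly a t-test on change, so this ratio applies to it directly. Change scores need 1/0.65, 1/0.75 or 1/0.85 times as many subjects, which is 54%, 33% or 18% more. Put the other way, ANCOVA with 26, 30 or 34 completers (40 x ratio) matches a change analysis with 40.

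**Mean of the two NPRS follow-up times.**

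- Mean follow-up minus baseline: 1.5(1-r) = 1.05, 0.75, 0.45
- ANCOVA on mean follow-up: (1-r)(1+2r)/2 = 0.56, 0.50, 0.36
- Ratio: (1+2r)/3 = 0.53, 0.67, 0.80

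**Power.** The standard error of the arm difference is sqrt(2V/20), with V the variance above. Power comes from the noncentral t with 38 df for change and 37 df for ANCOVA. At r = 0.5 and one time point, the standard error is sqrt(2 x 1.00/20) = 0.316 for change and sqrt(2 x 0.75/20) = 0.274 for ANCOVA, in SD units.

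| Contrast | r = 0.3 | r = 0.5 | r = 0.7 |
|---|---|---|---|
| One time, change | 50% | 64% | 85% |
| One time, ANCOVA | 68% | 76% | 90% |
| Mean of both, change | 62% | 76% | 93% |
| Mean of both, ANCOVA | 87% | 90% | 97% |

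These powers ignore the small extra variance from estimating the covariate slope. A simulation of 10,000 two-time trials at r = 0.5 and a 0.8 SD difference gave 69% for change and 80% for ANCOVA; the formulas give 69% and 81%.

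**The case against.** **The planned test is not wrong.** Under randomisation the Strategy x Time interaction is unbiased and addresses RH2 directly. The Kruskal-Wallis test on difference scores in the Abstract is also a between-arm comparison of pain change. This stands: the issue is precision only, and it shrinks as r rises.

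**The Strategy main effect.** Because the Abstract lists main effects, a reader might infer that RH2 will be judged on that effect. It would then recover only 2/3 of a constant post-treatment difference on NPRS (two of three levels) and 1/2 on Oswestry (one of two), and for height it would be swamped by stature. The documents do not support that reading. RQ2 and RH2 concern changes, which are tested by the interaction; main effects include Time, which bears on RH1; and the hypothesis 2 text never says that the Strategy main effect decides anything. What remains is a missing clarification.

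**Size of the gain for pain.** A reader might set the 2-df interaction, with power 52/67/88% under the same assumptions, against ANCOVA of the mean follow-up score at 87/90/97%. That overstates the benefit, because part of the gap comes from using one degree of freedom and assuming an equal effect at both times. The matching 1-df change contrast has 62/76/93%, so adjustment itself adds about 25, 14 and 4 points.

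**Two separate time points.** If the immediate and 2-week NPRS are tested separately with Bonferroni (alpha 0.025 each), ANCOVA power per time is 56/66/83%. That is no better than the omnibus interaction at r = 0.5 and worse at r = 0.7. The objection stands as far as it goes, but the two tests answer different questions. The interaction does not say at which time the arms differ, and at alpha 0.025 the same noncentral t calculation gives change scores 38/52/76%. On matched contrasts, adjustment is ahead at every r examined.

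**Conclusion.** The concern holds as a matter of efficiency. The plan compares arms on change when a more precise comparison is available from data it already collects. On matched contrasts, the variance of the arm difference falls by 35/25/15% at one follow-up time and by 47/33/20% for the mean of both NPRS follow-ups, at r = 0.3/0.5/0.7.

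The ordering holds for any r between 0 and 1 under equal variances and a common correlation. The power figures depend on the assumed r, 0.75 SD difference and 1:1 allocation, none of which the documents state. This does not show a biased or invalid test, nor that the plan rests RH2 on the Strategy main effect. The change is worth making because it is nearly free in a trial of 40 completers.

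**What to change.** In Data Analysis, experimental hypothesis 2, for pain and function:

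1. Model the immediate and the 2-week NPRS on arm, with the pre-intervention Session 1 NPRS as covariate. Use the same NPRS item at each time and name it, since Session 1 collects current, minimum, maximum and average ratings. State whether the 2-week value is the one taken on arrival or after the Session 2 intervention, as both are collected.
2. Model the 2-week Oswestry on arm, with the Session 1 Oswestry as covariate.
3. Alternatively, use a repeated-measures model that keeps baseline as an outcome but gives both arms a common baseline mean. It recovers about the same precision.
4. Report the adjusted arm difference with its 95% CI as the RH2 result for pain and function, and say whether the two NPRS times are tested separately (with the Bonferroni correction) or as their mean.
5. Add one line: RH2 is not judged on the Strategy main effect, which would average in the pre-treatment value.

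The cost is analysis wording and one degree of freedom (37 instead of 38). No new data or visits are needed. The three-level Time factor for function must in any case be reconciled with the two scheduled Oswestry administrations, which is a separate point.
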